6.1. Primary Endpoint

6.1.1. Loss of Response

6.1.1.1. Primary Analysis

- Summary: Time to loss of response (or protocol-defined flare) as measured from date of first dose of randomized treatment until the date of protocol-defined flare as recorded on the CRF.
- Population: FAS-RA.
- Statistical Method: Analyses for Time to Event Data in [Section 5.2.4](#). Probabilities of not having had the event will be reported at Week 52. Pairwise differences in these probabilities between treatments and their 95% CIs will also be reported. Hazard ratios and their 95% CIs will also be reported.
- Missing Data: See [Section 5.3.3](#).

6.1.1.2. Additional/Supportive Analyses

Additional analysis of the loss of response would be as:

- The time to loss of response will be analyzed using the methods in [Section 5.2.4](#) for the PPAS population.
- Missing time to loss of response will be multiply imputed under censoring not at random under a tipping point analysis framework using the methods in [Section 5.2.4](#) and [Appendix 6](#) for the FAS-RA population.

6.2. Key Secondary Endpoint

6.2.1. Loss of Response Based on the IGA Score

6.2.1.1. Primary Analysis

- Summary: Time to loss of response based on achieving IGA ≥ 2 (for the first time) as measured from date of first dose of randomized treatment until the last dose of randomized treatment (if not entered rescue) or first day of rescue treatment (if entered rescue).
- Population: FAS-RA.
- Statistical Method: Analyses for Time to Event Data in [Section 5.2.4](#). Probabilities of not having had the event will be reported at Week 52.
- Missing Data: See [Section 5.3.3](#).

6.2.1.2. Additional/Supportive Analyses

Additional analysis of the loss of response based on the IGA score would be as:

- The time to loss of response based on the IGA score will be analyzed using the methods in [Section 5.2.4](#) for the PPAS population.

6.3. Secondary Endpoints (Efficacy)

6.3.1. Response Based on (IGA, EASI-50, EASI-75, EASI-90, EASI-100, NRS4 for Severity of Pruritus, SCORAD50 and SCORAD75, IGA + EASI-75)

	All Randomized Subjects	Randomized Subjects Requiring Rescue Treatment	Pre- Randomization Subjects
Summary	Proportion of subjects achieving a response at Weeks 12, 16, 28, 40 and 52	Proportion of subjects achieving a response at Rescue Weeks 2, 4, 8 and 12	Proportion of subjects achieving a response at Weeks 2, 4, 8 and 12
Population	FAS-RA	FAS-RE	FAS-OL
Baseline	Study (see Section 3.4)	Rescue (see Section 3.4)	Study (see Section 3.4)
Statistical Method	CMH and normal approximation as in Section 5.2.1 .	Normal approximation as in Section 5.2.1 .	Normal approximation as in Section 5.2.1 .
Missing Data	Missing values after dropout are defined as “non-response” (see Section 5.3.1)	Missing values after dropout are defined as “non-response” (see Section 5.3.1)	Missing values after dropout are defined as “non-response” (see Section 5.3.1)

6.3.2. Change from Baseline in (Total EASI Score, SCORAD (VAS) Pruritus and Sleep Sub-Scales, PP-NRS for Severity and Percent BSA)

	All Randomized Subjects	Randomized Subjects Requiring Rescue Treatment
Summary	Change from baseline at Weeks 12, 16, 28, 40 and 52	Percent change/Change from baseline at Rescue Weeks 2, 4, 8 and 12
Population	FAS-RA	FAS-RE
Baseline	Study (for Week 12); Randomization (for visits after Week 12) (see Section 3.4)	Rescue (see Section 3.4)
Statistical Method	MMRM as in Section 5.2.2	MMRM as in Section 5.2.2
Missing Data	Use observed data (see Section 5.3.2)	

Change from Study Baseline at Week 12 and its 95% CI will be estimated for each randomized treatment group using an MMRM analysis using data from Weeks 2, 4, 8 and 12. For PP-NRS, data will be included from Days 2 – 15, Weeks 4, 8 and 12.

6.4. Secondary Endpoints (PRO)

6.4.1. Change from Baseline in (HADS, POEM, PSAAD and DLQI/CDLQI)

Summary	Change from baseline at Weeks 12, 16, 28, 40 and 52
Population	FAS-RA
Baseline	Study (for Week 12); Randomization (for visits after Week 12) (see Section 3.4)
Statistical Method	MMRM as in Section 5.2.2
Missing Data	Rules, if any, suggested by the developers of these instruments will be followed in calculating the outcome value in the presence of missing data. If these rules are not enough for defining an outcome value, then the missing values will be handled in the same way as other continuous variables. (see Section 5.3.2)

Change from Study Baseline at Week 12 and its 95% CI will be estimated for each randomized treatment group using an MMRM analysis using data from Weeks 2, 4, 8 and 12. For PSAAD, weekly data will be included from Weeks 1 – 12.

6.4.2. Response Based on PtGA

Summary	Proportion of subjects achieving a response at Weeks 12, 16, 28, 40 and 52
Population*	FAS-RA
Baseline	Study (see Section 3.4)
Statistical Method	CMH and normal approximation as in Section 5.2.1
Missing Data	Missing values after dropout are defined as “non-response” (see Section 5.3.1)

* For endpoints that are defined based on meeting a threshold for a visit value or change from baseline, only subjects with a baseline value above that threshold will be included (see [Section 3.3](#)).

6.5. Subset Analyses

Summary statistics for the primary endpoint will be presented by subgroups as below:

- Age (years) group (<18, ≥18; <40, ≥40; <65, ≥65);
- Sex (Male, Female);
- Race (White, Black or African American, Asian, Other¹);
- Weight (kg) group (<70, 70-100, >100);
- Responder based on IGA + EASI-75 (before Week 8, at Week 8, after Week 8);
- Region of enrollment (US/Canada, Eastern Europe, Western Europe, Asia, Latin America);
- AD Duration (years) group (<26, ≥26);
- Study Baseline disease severity based on IGA score (moderate, severe);
- Randomization Baseline IGA score;
- Study Baseline EASI group (16-25, >25);

¹ For purposes of analysis, Other will comprise the categories of American Indian or Alaska Native, Native Hawaiian or Other Pacific Islander, Multi-Racial and any other category reported on the CRF.

- Study Baseline % BSA group (10-30, >30-50, >50);
- Prior (to Study Baseline) use of systemic immunosuppressant for AD (Yes, No).

Pairwise treatment comparisons using the hazard ratio and its 95% confidence interval will be presented for each defined category of each subgroup. No p-values will be presented.

The primary purpose of the subgroup analyses is to check for consistency of results across subgroups, to make sure overall results are not being driven by some subset of subjects. There is no intention to have any specific inference within subgroups.

6.6. Baseline and Other Summaries and Analyses

6.6.1. Baseline Summaries

Demographics, medical history, primary diagnosis and prior treatments for atopic dermatitis collected during Visit 1/Screening will be summarized according to CaPS. Baseline disease severity based on IGA, baseline EASI score and baseline BSA will also be summarized by gender and by age group (adults and adolescents). Summaries will be displayed for each of the FAS analysis sets (see [Sections 4.1](#) and [4.3](#)) only.

6.6.2. Study Conduct and Subject Disposition

Subjects evaluation, disposition, discontinuation will be summarized according to CaPS. Summaries will also be displayed for each of the SAF analysis sets (see [Sections 4.1](#) and [4.3](#)). A listing of all subjects whose study participation was impacted by COVID-19 and subject discontinuations due to COVID-19 will be displayed.

6.6.3. Study Treatment Exposure

A summary of compliance by study period will be provided.

The exposure to study drug will be summarized by the total number of days of dosing, and number and percentage of subjects who were not compliant (<80% or >120%) with the dosing schedule.

Summaries will be displayed for each of the SAF analysis sets (see [Section 4.3](#)).

6.6.4. Concomitant Medications and Non-Drug Treatments

Prior drug and non-drug treatment, general concomitant drug and non-drug treatment will be summarized according to CaPS.

For SAF-OL, only summaries of prior drug treatments for primary diagnosis and non-drug treatments will be displayed. For SAF-RA and SAF-RE, only summaries of general concomitant drug treatments will be displayed. Concomitant drug treatments for primary diagnosis and non-drug treatments will be displayed for each of the SAF analysis sets.

6.7. Safety Summaries and Analyses

Safety analysis will be based on the SAF analysis sets (see [Section 4.3](#)). The SAF-OL analysis set will be used to summarize the safety experience for all subjects during the first 12 weeks of open label treatment with PF-04965842 200 mg QD using the Study Baseline (see [Section 3.4](#)). The SAF-RA analysis set will be used to summarize the safety experience for all randomized subjects using the Randomization Baseline. Subjects who report a protocol-defined flare and get rescue treatment will be censored at the day before the first day of rescue in this analysis. All subjects will be classified according to the actual treatment regimen they received. The SAF-RE analysis set will be used to summarize the safety experience for the subjects who receive rescue treatment using the Rescue Baseline. Study Baseline will be used for all displays of results meeting lab abnormality criteria, throughout the subject's study experience.

All clinical AEs, SAEs, treatment-emergent signs and symptoms (TEAEs), withdrawal due to AEs, ECGs, vital signs and safety laboratory data will be summarized to evaluate the safety of subjects.

Safety data will be presented in tabular and/or graphical format and summarized descriptively, where appropriate. All safety endpoints will be listed and summarized in accordance with Pfizer Standards. Categorical outcomes (eg, AEs) will be summarized by subject counts and percentage. Continuous outcome (eg, blood pressure, pulse rate, etc.) will be summarized using N, mean, median, standard deviation, etc. Change from baseline in laboratory data, ECGs and vital signs will also be summarized. Subject listings will be produced for these safety endpoints accordingly. Separate summaries will be displayed for adjudicated data on cardiovascular (CV), malignancy, opportunistic infection, histopathologic and hepatic events.

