### **5.2. Rescue Treatment**

Subjects will be instructed to contact the site if they experience a significant worsening of their atopic dermatitis, such as a recurrence of pruritus, during the double-blind treatment period. Site staff will determine if the subject should return to the site for an unscheduled (see [Section 6.5.1](#)) or regularly scheduled visit (see [Section 6.3](#)). Subject will be reminded not to take study drug on the day of the site visit. At the visit (regular or unplanned) the subject will be assessed for flare, defined as a loss of at least 50% of the EASI response at Week 12 and an IGA of 2 or higher. Subjects who meet the definition of flare are to receive rescue treatment that day and enter an open-label rescue period during which they receive 12-weeks of 200 mg PF-04965842 QD with concomitant topical therapy per SOC. See [Section 5.2.1](#) for guidance on topical therapies.

After completing the rescue period, subjects are allowed to enter the LTE study B7451015, if eligible. If a subject discontinues prematurely or is not eligible or willing to participate in B7451015, then the subject enters the 4-week, untreated follow-up safety period. Refer to [Schedule of Activities for Rescue Treatment](#).

Subjects not meeting the definition of flare will continue on their blinded treatment. Physicians may continue to clinically evaluate for flare using the EASI and IGA assessments at their discretion.

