#### **6.5.1. Rescue Treatment - Flare Occurring at an Unplanned Visit (Rescue Visit 1, Day 1/Week 0 (±3 days))**

- Administer and score the Since Last Visit C-SSRS. For subjects meeting any of the criteria specified in [Section 7.5.1](#) a risk assessment by a qualified MHP should be done to determine whether it is safe for the subject to continue to participate in the trial;
- Administer PROs including: PtGA, DLQI (or CDLQI), POEM, HADS, EQ-5D-5L (or EQ-5D-Y in select countries), SF-36v2, Acute and FACIT-F (or Peds-FACIT-F). SF-36v2 will be completed by adult subjects only;
- Adolescents 12-17 years of age will not complete the SF-36v2. Adolescents 12-17 years of age will complete the CDLQI instead of the DLQI, the EQ-5D-Y in select countries instead of the EQ-5D-5L and Peds-FACIT-F instead of the FACIT-F;

- Review PSAAD daily completion (in selected countries) and pruritus NRS completion for this visit in the eDiary. Instruct the subject that the pruritus NRS completion will be collected daily in the eDiary from Days 1-15 during rescue treatment and then only on study visit days at the investigator site thereafter. PSAAD will be completed daily (in selected countries) in the eDiary from Day 1 through the EOS visit during rescue treatment. Review eDiary procedures with subject as necessary;
- Obtain weight for all subjects and height for adolescents only (12 to <18 years old);
- Conduct targeted physical examination;
- Obtain vital signs including pulse rate, blood pressure, respiratory rate and oral or tympanic temperature (after at least 5 minutes of rest);
- Perform a single 12-lead ECG;
- Conduct clinical evaluations including IGA, SCORAD, EASI and BSA (calculated in the EASI);
- Obtain fasting samples for laboratory testing: serum chemistry, hematology (including coagulation, RBC/WBC Indices, lymphocyte subsets and markers), lipid profile, and urinalysis;
-  
- Following one year of total exposure to study drug since the last TB test, all subjects in regions which are above a low risk for Tuberculosis (ie, >10/100,000 prevalence) will undergo tuberculosis (TB) testing. If so, ensure testing is performed as per [Section 7.3.4](#). A negative test result for tuberculosis is required for ongoing eligibility for study participation;

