### **7.8. Patient-Reported Outcomes (PROs)**

Subjects will complete PROs and AD clinical assessments at the clinic in the order they are presented in the electronic tablet (ePRO device). All PROs and AD clinical assessments should be completed prior to other clinical activities and investigator product administration. Results of clinical assessment of AD should not be shared with the subject until they have completed their PROs. The PROs should be checked for completeness by the study site staff before proceeding with other steps of the clinical visit procedures. Compliance with scheduled PROs activities will be monitored. Delegated site staff will oversee the administration of PROs at site visits to ensure protocol compliance. Subjects are given a handheld device to complete the pruritus NRS and PSAAD on a daily basis. Delegated site staff will review compliance at each visit and counsel as appropriate. If a subject has repeated non-compliance, the subject should be re-trained on the device. If a subject is unable to complete the PROs on the handheld device due to documented difficulty using the technological devices or other limitation, the subject will be permitted to enter or remain in

the study. In the event of electronic malfunction, a replacement device will be shipped to the site.

Some examples of the validated paper versions of Patient Reported Outcomes instruments are included in the Appendices of this protocol. In instances where an electronic device is used to collect the PRO data, the electronic version may differ slightly in format or wording compared with the paper version to facilitate electronic implementation.

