requested by Pfizer Safety to obtain specific follow-up information in an expedited fashion. This information is more detailed than that recorded on the CRF. In general, this will include a description of the event in sufficient detail to allow for a complete medical assessment of the case and independent determination of possible causality. Any information relevant to the event, such as concomitant medications and illnesses, must be provided. In the case of a subject death, a summary of available autopsy findings must be submitted as soon as possible to Pfizer Safety. Any pertinent additional information must be reported on the CT SAE Report Form; additional source documents (eg, medical records, CRF, laboratory data) are to be sent to Pfizer Safety **ONLY** upon request.

Any clinically significant worsening of AD is considered an AE regardless of meeting the definition of flare.

As part of ongoing safety reviews conducted by the sponsor, any non-serious AE that is determined by the sponsor to be serious will be reported by the sponsor as an SAE. To assist in the determination of case seriousness, further information may be requested from the investigator to provide clarity and understanding of the event in the context of the clinical study.

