### **8.2. Definitions**

#### **8.2.1. Adverse Events**

An AE is any untoward medical occurrence in a study subject administered a product or medical device; the event need not necessarily have a causal relationship with the treatment or usage. Examples of AEs include, but are not limited to:

- Abnormal test findings;
- Clinically significant signs and symptoms;
- Changes in physical examination findings;
- Hypersensitivity;
- Progression/worsening of underlying disease;
- Drug abuse;
- Drug dependency.

Additionally, AEs may include signs and symptoms resulting from:

- Drug overdose;
- Drug withdrawal;
- Drug misuse;
- Drug interactions;
- Extravasation;
- Exposure during pregnancy (EDP);
- Exposure via breastfeeding;
- Medication error;

- Occupational exposure.

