3.5.1. Adverse Events

An adverse event is considered TEAE to a given treatment if the event started during the effective duration of treatment. All events that start on or after the first dosing day, but before or on the last dosing day plus the lag time (28 days) will be flagged as TEAEs. The algorithm will not consider any events that started prior to the first dose date.

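### A flare AE dated at the flare visit is moved from the randomized arm to open-label rescue 200 mg, and earlier-dated flare AEs put the primary endpoint into the by-arm TEAE totals

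*SAP*

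**What the plan says.** **Flare as an AE.** Protocol 8.1: "Any clinically significant worsening of AD is considered an AE regardless of meeting the definition of flare". The list of AE examples in Protocol 8.2.1 also includes "Progression/worsening of underlying disease".

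**Timing on the flare day.** Protocol 5.2: "Subjects who meet the definition of flare are to receive rescue treatment that day". Protocol 7.8 fixes the order within a visit: "All PROs and AD clinical assessments should be completed prior to other clinical activities and investigator product administration". The flare is therefore established before the first rescue dose, on the same date.

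**Attribution.** SAP 3.5.1: "An adverse event is considered TEAE to a given treatment if the event started during the effective duration of treatment". It then sets the limits by calendar day, with no reference to time of day: "All events that start on or after the first dosing day, but before or on the last dosing day plus the lag time (28 days".

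**End of the blinded safety window.** SAP 6.7, on SAF-RA: "Subjects who report a protocol-defined flare and get rescue treatment will be censored at the day before the first day of rescue in this analysis". The rescue set, SAF-RE, is summarized from there.

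**Display.** SAP section 6 shows safety by treatment group for SAF-RA only. Protocol 9.3 plans the rescue summaries by randomized regimen. SAP 6.7 reports AEs as subject counts and percentages, and neither SAP 6.7 nor 6.7.1 plans a total without AD worsening.

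**The concern.** Each rule is ordinary when read alone. Together they send the same clinical event to different tables according to the onset date that the site records.

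- **Dated at the visit, rescue the same day.** The event is cut from the blinded arm and appears as emerging on the 200 mg given to treat it.
- **Dated earlier.** The event stays in the blinded arm and counts towards that arm's TEAE total. If the drug prevents flares, these events fall more heavily on placebo.

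The blinded period is the trial's only randomized safety comparison. Its headline total would carry a share of the efficacy result, and that share would depend on a date convention the documents do not state. The rescue table would show AD worsening as treatment-emergent on rescue although it came first.

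The SAP is also not consistent with itself here. Section 3.4 lets Rescue Day 1 observations serve as Rescue Baseline, so one visit is before rescue for efficacy and on rescue for AEs. The problem does not arise at randomization: the last open-label dose is given at the Week 12 visit and blinded drug starts the next day (Protocol section 5), so a rule by date separates those two periods.

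**Working it through.** **1. Apply the rules by date.** Let the flare visit be day V and the first rescue dose day R. SAF-RA runs to R − 1, and rescue TEAEs start at R.

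| Onset of the flare AE | Rescue start | SAF-RA (by arm) | SAF-RE (rescue 200 mg) |
|---|---|---|---|
| before V | R = V | counted | not counted |
| on V | R = V (the instruction in Protocol 5.2) | dropped, since V > R − 1 | counted, since V ≥ R |
| on V | R after V | counted, since V ≤ R − 1 | not counted |

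The third row matters because Rescue Visit 1 has a window of ±3 days (Protocol 6.5.1). The 28-day lag in SAP 3.5.1 would have kept the second-row event with blinded treatment, but the censoring in SAP 6.7 overrides it. Each event goes to one table, never both.

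**2. Is there a stated figure to reproduce?** Not for AEs. The nearest design statement is 94% power for a ratio of medians of 1.5 with 200 per arm and 5% two-sided error (SAP 2.2). No event count, median or dropout rate is given, so the power cannot be reproduced from the stated inputs alone. With exponential times the hazard ratio is 1/1.5, and the Schoenfeld formula gives

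events = 4 × (1.960 + 1.555)² / (ln 1.5)² ≈ 301 per pair.

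If all 400 subjects in a pair had events, power would be 98.2%. I use 301 only to obtain flare rates of a plausible order.

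**3. Flare proportions (assumed).** Exponential times, 40 weeks, no dropout, both doses at the design ratio. With m the cumulative placebo hazard over 40 weeks, solve

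200 × (1 − e^−m) + 200 × (1 − e^(−m/1.5)) = 301, giving m = 1.7245.

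- Placebo: 1 − e^−1.7245 = 0.822, about 164 of 200.
- Each active arm: 1 − e^−1.1497 = 0.683, about 137 of 200.
- All arms: about 438 flares.

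**4. TEAE totals (assumed).** Every flare is recorded as an AE and rescued. Let q be the share of flare AEs dated at the visit with same-day rescue, p the flare proportion in an arm, and b the probability of any other TEAE, equal in all arms and independent of flare.

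- Any TEAE in a SAF-RA arm: 1 − (1 − b)(1 − p(1 − q)).
- Placebo minus active: (1 − b)(1 − q)(0.822 − 0.683).
- Any TEAE in SAF-RE, with the same b: 1 − (1 − b)(1 − q).

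| q | Flare AEs in SAF-RA, placebo / each active | Flare AEs in SAF-RE | Any-TEAE difference, b = 30% | b = 50% | Any TEAE in SAF-RE, b = 30% / 50% |
|---|---|---|---|---|---|
| 0 | 164 / 137 | 0 | 9.7 points | 6.9 points | 30% / 50% |
| 0.5 | 82 / 68 | 219 | 4.8 points | 3.5 points | 65% / 75% |
| 1 | 0 / 0 | 438 | 0 | 0 | 100% / 100% |

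The other-TEAE rate is the same in every arm, so the whole difference comes from the endpoint. At q = 1 every rescued subject has a rescue TEAE by construction.

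**The case against.** **Displays by term may separate AD.** SAP 3.5, 6.7 and 6.7.1 defer AE displays to sponsor and CDISC standards, and listings are promised. If AD worsening has its own row, a careful reader can see it. This stands in part. A row does not remove the event from the total, and it does not return a visit-dated flare to its randomized arm.

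**Onset will often precede the visit.** Subjects are told to contact the site when their disease worsens (Protocol 5.2 and 6.5), which suggests an earlier onset for flares prompted by symptoms. This is fair, and the split is unknown. It moves the effect from the rescue table to the by-arm totals without removing it.

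**Relapse after withdrawal is legitimate safety information.** This stands. These are all-causality tables, and calling their contents toxicity would go beyond the documents. The all-event table should stay, with a second total beside it.

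**Stronger readings that a reader might infer.**

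- *The totals could reverse the sign of a true excess on drug.* Suppose non-AD TEAE rates of 40% on placebo and 60% on 200 mg, with AD worsening recorded in 80% and 20%. If no AD AE is visit-dated, the totals are 1 − 0.6 × 0.2 = 88% and 1 − 0.4 × 0.8 = 68%, so +20 points becomes −20. None of these rates is in the documents. If all AD AEs are rescued flares, the same rates give 76% v 66% (−10) at 25% visit-dated, 64% v 64% (0) at 50%, and 52% v 62% (+10) at 75%. The −20 needs exactly the case in which nothing is charged to rescue.
- *Severe-AE and discontinuation totals are distorted too.* SAP 6.7.1 names no severe-AE table. A protocol-defined flare leads to rescue with study drug, and nothing shows that it is counted as a discontinuation due to an AE.
- *All Rescue Day 1 events before the first dose can be reassigned.* That needs AE onset times, and the documents do not show that they are collected.

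**Conclusion.** The point holds at the level of dates. If the SAP is followed as written, a flare AE dated at the visit with same-day rescue is dropped from the randomized arm in which it arose and counted as a TEAE of open-label rescue 200 mg, in a table that the SAP does not split by arm. No other passage corrects this. Flare AEs with an earlier onset make the by-arm any-TEAE totals partly a restatement of the primary endpoint.

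The direction of the second effect follows if active treatment prevents flares: the placebo total rises relative to the active arms. Its size cannot be fixed from the documents. The range of 0 to about 10 points rests on the assumed inputs in the working: 301 events per pair, exponential times, no dropout, every flare recorded as an AE and rescued, and other TEAEs at 30% to 50% in every arm. A treatment effect larger than the design ratio would widen it.

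The primary efficacy analysis is not affected. This is a reporting rule that should be corrected before unblinding. The documents do not support a claim that the safety comparison will be reversed.

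**What to change.** **Attribution (SAP 3.5.1 and 6.7).** Assign the AD-worsening AE that triggered rescue to the blinded period and exclude it from SAF-RE TEAEs. Identify it by matching to the flare date, which SAP 6.1.1.1 says is recorded on the CRF. Extend the rule to other Rescue Day 1 events only where an onset time before the first rescue dose is recorded. Visit-dated flare AEs charged to rescue then fall to zero, whatever the true rates.

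**Display (SAP 6.7.1).** Add one by-arm SAF-RA any-TEAE summary that excludes AD-worsening terms, beside the all-event table. List the excluded terms before unblinding.

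**Consistency.** State the onset-date convention for AD worsening, and reconcile SAP section 6 with Protocol 9.3 on whether rescue safety is shown by randomized regimen.

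**Cost.** SAP wording, one derivation rule and one table. Matching the triggering AE needs only AE dates and the flare date. The downside is a second TEAE total to explain. No visit, dose or clinical rule changes.

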#### **4.4. Lifestyle Requirements**

In order to participate in the study, subjects must be aware of the following lifestyle guidelines and restrictions that apply during and after the treatment period.

- On study visit days: Day 1, Weeks 4, 12, 52 and End of Study (EOS) and corresponding visits if a subject enters the rescue treatment period, subjects must comply with fasting requirement for at least 8 hours prior to the visit. Water and permitted non-study medications are allowed (see [Section 5.9.1](#)).
- On study visit days, subjects must not smoke or ingest caffeine during the 30 minutes prior to blood pressure and heart rate measurements.
- On study visit days, subjects must not take the dose of investigational product until instructed to do so by the investigator or designated study site staff.

- On study visit days, showering or bathing is permitted prior to attending the study visit, but subjects must not moisturize or apply emollient. Non-medicated emollient is allowed after the visit. Discontinue and avoid using certain medications and treatments ([Section 4.2](#), [Section 5.9.2](#), and [Appendix 3](#)).
- Agree to use one highly effective method of contraception (as specified in [Section 4.4.1](#), as applicable).

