6. ANALYSES AND SUMMARIES

Treatment comparisons will only be displayed for the FAS-RA analysis set where it is relevant. Pairwise comparisons will be reported among the treatment groups. No treatment comparisons are relevant for the FAS-OL and FAS-RE analysis sets. Similarly, safety data displays will be by treatment group only for SAF-RA and not for SAF-OL or SAF-RE.

A summary of analyses for clinical efficacy endpoints is provided in [Appendix 1](#). Visit windows to be used for all efficacy analyses and some relevant safety analyses are detailed in [Appendix 2](#).

Efficacy and PRO data collected at the Week 16/Week 56 follow-up visits or at the Rescue Visit Week 16 follow-up visit will be displayed in listings only, and will not be part of any analyses, unless specifically noted otherwise.

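### SAP 6.7 cuts randomized-period safety data the day before rescue, so when rescue starts at the flare visit, that visit's labs, ECG and vital signs are not summarized by arm

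*SAP*

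**What the plan says.** - **The cut.** SAP 6.7, on the SAF-RA safety summaries: "Subjects who report a protocol-defined flare and get rescue treatment will be censored at the day before the first day of rescue in this analysis".
- **Start of rescue.** Protocol 5.2: "Subjects who meet the definition of flare are to receive rescue treatment that day and enter an open-label rescue period". The same section says of that visit: "Subject will be reminded not to take study drug on the day of the site visit". Protocol 4.4 adds that on visit days "subjects must not take the dose of investigational product until instructed to do so by the investigator".
- **What is measured.** Protocol 6.5.1 (Rescue Visit 1, Day 1) lists vital signs, then "Perform a single 12-lead ECG", then "Obtain fasting samples for laboratory testing: serum chemistry, hematology (including coagulation, RBC/WBC Indices, lymphocyte subsets and markers), lipid profile, and urinalysis". Giving the study drug comes later in the list.
- **Where the values go.** SAP 3.4 and Appendix 2 define Rescue Baseline as the last value from the final blinded dose up to and including the first rescue day. SAP 6.7 uses that baseline for the rescue set, SAF-RE.
- **What is shown by arm.** SAP 6: "safety data displays will be by treatment group only for SAF-RA and not for SAF-OL or SAF-RE". Protocol 9.3 instead says that safety data for rescued subjects will be summarized by the regimen to which they were randomized.

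**The concern.** A subject who starts rescue at the flare visit has had no rescue drug when that visit's safety measurements are made. The visit is their last look at randomized treatment. The SAP assigns it to the rescue period, and the rescue period is shown pooled.

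The removal is triggered by the primary endpoint. If flare rates differ between arms, the by-arm lab, ECG and vital-sign summaries lose records at different rates, and those records come from the subjects who flared. A subject who reaches Day 365 without flaring keeps the Day 365 values in the by-arm display. A subject whose flare is found that day does not.

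Early values matter here. Protocol 1.2.4 reports dose-dependent platelet decreases that plateaued at Week 4, so the first laboratory values after randomization to 200 mg, 100 mg or placebo are informative about the arms.

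**Working it through.** The plan states no figure on this point. The check lays the SAP date rule over the visit calendar and then looks at scale.

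**Step 1: scheduled visits.** Inputs are the target days in the Schedule of Activities: 85 (Week 12), 113, 197, 281 and 365. For a flare found on day *d* with rescue that day, the cut is *d* − 1. The last scheduled value kept in SAF-RA is the latest target day not after the cut.

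| Flare found at | Cut | Last scheduled value kept by arm | Days lost |
|---|---|---|---|
| Week 16, Day 113 | 112 | Day 85 | 113 − 85 = 28 |
| Week 28, Day 197 | 196 | Day 113 | 197 − 113 = 84 |
| Week 40, Day 281 | 280 | Day 197 | 281 − 197 = 84 |
| Week 52, Day 365 | 364 | Day 281 | 365 − 281 = 84 |

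In the first row the value kept is the Week 12 randomization visit, so no scheduled post-randomization value remains.

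**Step 2: unscheduled flare visits.** SAP Appendix 2 applies windows to lab data summarized by visit and keeps the record nearest the target day. The post-randomization windows are Days 100–155, 156–239, 240–323 and 324–379. Week 12 ends at the first randomized dose.

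- A flare on Days 86–99 generally falls in no post-randomization window: 14 days.
- A flare on Days 114–155, 198–239 or 282–323 loses its window to a scheduled visit made on target: 3 × 42 = 126 days.
- Together, 14 + 126 = 140 of the 279 days from Day 86 to Day 364.

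On those 140 days the flare-visit labs would be absent from by-visit tables even without the cut. On the other 139 days the cut is what removes them. Abnormality displays are affected on any day. The SAP 6.7 sentence on lab abnormality criteria fixes their baseline and gives no exemption from the cut.

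**Step 3: scale, on assumptions.** The documents give 200 subjects per arm, 94% power, two-sided 5% and a median ratio of 1.5, but no flare rates or event count. Assume exponential flare times, no dropout and hazard ratio 1/1.5.

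- Events for 94% power (Schoenfeld): 4 × (1.960 + 1.555)² / (ln 1.5)² ≈ 301 in two arms.
- Flares in 40 weeks in an arm with median *m* weeks: 200 × (1 − 2^(−40/*m*)). A total of 301 is reached at a placebo median of about 16.1 weeks, giving about 164 placebo and 137 active flares.
- Flares in the first 4 weeks: 200 × (1 − 2^(−4/*m*)), about 32 placebo and 22 active.
- For placebo medians from 8 to 40 weeks, total flares run from 194 to 100 on placebo and from 180 to 74 on active.
- If flare proportions were instead 50–80% on placebo and 10–40% on 200 mg, the counts would be 100–160 and 20–80.

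These are counts of flares. They are upper limits on records lost from by-visit lab tables (Step 2), and they assume same-day rescue throughout.

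**Step 4: same visit, two rules.** For the key secondary endpoint, SAP 6.2.1.1 follows rescued subjects through the first rescue day. The flare visit therefore counts for randomized-arm efficacy but not for randomized-arm safety summaries.

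**The case against.** Several stronger readings are tempting, and the documents do not support them.

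- **That the data are discarded, or can never be seen by arm.** They remain in subject listings and as Rescue Baseline, and Protocol 9.3 promises by-regimen summaries of rescued subjects. But SAP 2 allows the SAP to modify the protocol's plans, and SAP 6 excludes those summaries. The gap in the SAP's summaries stands, and so does the conflict.
- **That every flared subject is affected.** The loss needs rescue to start on the visit day. Protocol 5.2 says so, but Protocol 6.5 does not repeat the timing, and Rescue Visit 1 carries a ±3-day window. After a later start the flare visit stays in SAF-RA.
- **That each flare costs a full assessment set.** Step 2 shows otherwise for by-visit lab tables. A subject who flares before the Week 16 visit has no scheduled post-randomization visit under any rule. ECG and vital signs use windows only if required.
- **That the cut contradicts SAP 6.7.2, which follows labs to the end of randomized treatment.** With no dose before the visit, the last blinded dose is normally the day before, so the cut can be read as that end. The value describing the subject at that point is still the one left out.
- **That suicidality ratings are lost from planned summaries.** The SAP's safety sections name no such summary.

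The timing objection has some force. At Rescue Visit 1 only the pregnancy test is expressly required before dosing; for labs, ECG and vital signs the order of the list implies it. The SAP, however, already treats the Rescue Day 1 record as pre-rescue by defining it as Rescue Baseline. It is also fair that the cut is a conservative convention that keeps rescue-day data out of the randomized arms, and that the displays are descriptive.

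**Conclusion.** The point holds for labs, ECG and vital signs of subjects who start rescue on the flare-visit day. Measurements that reflect randomized treatment only are left out of the SAP's by-arm summaries, and SAP 6 and Protocol 9.3 disagree on whether rescued subjects are shown by regimen.

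The firm part of the size is the calendar: 28 days of scheduled follow-up lost by arm for a Week 16 flare, 84 days for a flare found at Week 28, 40 or 52, and no scheduled post-randomization value in the Week 16 case. For unscheduled visits the effect on by-visit lab tables is smaller. The number of subjects and the imbalance between arms cannot be fixed from the documents. At the only stated effect, a median ratio of 1.5, the illustrative flare counts are fairly close (about 164 and 137); a wide imbalance needs flare rates that the plan does not state.

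A reader might infer that the safety conclusions are biased, but the documents do not show that. No efficacy inference or safety test depends on this rule. It should be corrected because the correction is simple and the omission depends on the outcome.

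**What to change.** In SAP 6.7, add that for labs, ECG and vital signs the record used as Rescue Baseline is also included in SAF-RA as the last assessment on randomized treatment, excluding any value documented as taken after the first rescue dose. Adverse events starting on Rescue Day 1 stay with the rescue period. Because the rule points to the Rescue Baseline record, it also works when rescue starts after the flare visit, and it does not depend on clock times for every measurement.

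Separately, reconcile SAP 6 with Protocol 9.3 on whether SAF-RE safety data are displayed by randomized regimen.

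The cost is a short SAP edit and a small programming change, with no new data collection. The downside is that a few same-day values will enter SAF-RA with pre-dose timing inferred from visit order.
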